#### **4.5 Study design**

This is a non-interventional, multinational, multi-centre, prospective, single-treatment arm, observational PASS in AGHD patients. The study will, under routine clinical practice conditions, investigate the long-term safety of Sogroya® (somapacitan), including but not limited to the occurrence of neoplasm, development of type 2 diabetes and medication errors.

Moreover, the titration regimen and clinical parameters of Sogroya® (somapacitan) therapy in AGHD patients will be collected and evaluated, when available as part of routine clinical practice.

Patients will be treated with commercially available Sogroya® (somapacitan) according to local practice at the discretion of the physician.

Protocol  
 Study ID: NN8640-4515  
 UTN: U1111-1264-8642  
 EU PAS No: Pending

**CONFIDENTIAL**

Date: 15 February 2022 **Novo Nordisk**  
 Version: 3.0  
 Status: Final  
 Page: 12 of 53

The duration of the study is planned with patient participation for 5 years or longer up to a total study duration of 10 years, if possible. The main purpose of the study is to observe patients for long-term safety.

## 4.6 Population

Approximately 400 patients with AGHD will be included globally.

### 4.6.1 Inclusion criteria

For an eligible patient, all inclusion criteria must be answered “yes”.

1. Signed consent obtained before any study-related activities (study-related activities are any procedure related to recording of data according to the protocol).
2. The decision to initiate treatment with commercially available Sogroya® (somapacitan) has been made by the patient and the treating physician before and independently from the decision to include the patient in this study.
3. Male or female, age above or equal to 18 years assigned to Sogroya® (somapacitan) treatment at the time of signing informed consent.
4. Diagnosis of adult growth hormone deficiency (AGHD) as per local practice

### 4.6.2 Exclusion criteria

For an eligible patient, all exclusion criteria must be answered “no”.

1. Previous participation in this study. Participation is defined as signed informed consent
2. Mental incapacity, unwillingness or language barriers precluding adequate understanding or cooperation
3. Patient with hypersensitivity to the active substance or to any of the excipients.
4. Patient with active malignancy or in treatment for active pre-existing malignancy.
5. Patient with acute critical illness, suffering from complications following open heart surgery, abdominal surgery, multiple accidental trauma, acute respiratory failure or similar conditions per investigator judgement.

## 4.7 Variables

Data within safety (AEs), clinical parameters and PRO questionnaires will be collected. Data and results from assessments and laboratory analyses will be recorded if performed according to routine clinical practice or physician discretion at the participating sites.

## 4.8 Data sources

Relevant data and results available in the patient’s medical record and from assessments and laboratory analyses performed according to routine clinical practice at the participating sites will be recorded in the eCRF.

## 4.9 Study size

The study is planned for the sample size of 400 patients.

Protocol  
 Study ID: NN8640-4515  
 UTN: U1111-1264-8642  
 EU PAS No: Pending

**CONFIDENTIAL**

Date: 15 February 2022  
 Version: 3.0  
 Status: Final  
 Page: 13 of 53

**Novo Nordisk**

#### 4.10 Data analysis

Adverse drug reactions will be analysed using descriptive statistics based on the ‘on-treatment’ observation period (primary evaluation) and ‘in-study’ observation period (secondary evaluation) within the study period. The Adverse drug reactions (ADRs) will be summarised by treatment, MedDRA (Medical Dictionary for Regulatory Activities) system organ class (SOC) and MedDRA preferred term (PT).

Incidence rates will be calculated for the endpoints Neoplasm and Diabetes Mellitus type 2.

## 5 Amendments and updates

Amendment or update no	Date	Section of study protocol	Amendment or update	Reason
1	21-Oct-2021	General update of the protocol	update	following PRAC review
2	15-Feb-2022	Minor updates to sections: “PASS information”, 9.1 and 9.7	update	following 2 nd -round PRAC review

## 6 Milestones

Milestone	Planned date
Registration in the EU PAS Register	Prior to start of data collection, i.e., before FPFV
Start of data collection – first patient first visit (FPFV)	15 Dec 2022
Interim report 1	Data cut 3 years following FPFV 15 Dec 2025
Last patient first visit – end of study recruitment	15 Dec 2027
Interim report 2	Data cut 6 years following FPFV 15 Dec 2028
Last patient last visit (LPLV)	15 Dec 2032
End of data collection (defined as database lock)	Q1 2033
Final report of study results	Q1 2034
Study progress reports	To follow PSUR timelines

Protocol  
 Study ID: NN8640-4515  
 UTN: U1111-1264-8642  
 EU PAS No: Pending

CONFIDENTIAL

Date: 15 February 2022  
 Version: 3.0  
 Status: Final  
 Page: 14 of 53

Novo Nordisk

## 7 Rationale and background

Sogroya® (somapacitan) is a recombinant human GH analog developed by Novo Nordisk, indicated for replacement of endogenous GH in AGHD. Replacement therapy with recombinant GH is the standard of care for patients with AGHD. Sogroya® (somapacitan) is a long-acting GH product developed for once weekly subcutaneous (s.c.) administration.

Replacement therapy with once-weekly somapacitan and once-daily somatropin differ from endogenous GH release under normal physiological conditions.

In clinical phase 3 trials, IGF-I levels obtained with somapacitan were within the age-adjusted normal reference range with temporary peaks above the upper limit of normal range for a small subset of patients. Importantly, modestly and transiently elevated IGF-I levels in GH replacement therapy have not been linked to adverse effects in published literature nor in the somapacitan phase 3 trials.

Even after over 20 years of adult GH replacement, evidence suggesting that rhGH replacement in adults increases cancer risk or accelerates recurrences of tumours in the hypothalamic-pituitary region remains unclear; With conflicting results in the literature, the overall effect of rhGH replacement on the development of diabetes is also unclear. Somapacitan has been studied in AGHD patients for up to 86 weeks. Thus, the safety information during longer period of treatment is limited.

If patients taking GH replacement report significant QoL benefits and/or there are objective improvements, such as in cardio-vascular risk markers, BMD, body composition, or physical activity tolerance, then GH treatment can be continued indefinitely. Therefore, further investigations, including long-term surveillance studies after regulatory approval are essential to improve our understanding of the safety and effectiveness of prolonged exposure to Sogroya®.

As part of the marketing authorisation of Sogroya®, Novo Nordisk has received a requirement from the Committee for Medicinal Products for Human Use (CHMP) under European Medicines Agency (EMA) to conduct a non-interventional PASS to investigate long-term safety of Sogroya® in patients with AGHD.

Therefore, as part of the risk management plan for Sogroya® (somapacitan) as treatment of AGHD, the primary aim of this NIS is to characterise the long-term safety profile of Sogroya® (somapacitan) with special focus on the important potential risks (diabetes mellitus type 2, neoplasms and medication errors) and additional long-term safety information. Therefore, this PASS may allow a further evaluation of these potential risks in relation to treatment with Sogroya®. Medication errors are of specific interest since some patients will switch from daily GH injections to weekly injections with Sogroya®. Therefore, the PASS may provide information on whether this might lead to medication errors in clinical practice.

The secondary aim is to investigate the clinical parameters in patients treated with Sogroya® (somapacitan) on body composition, metabolic parameters, skeletal integrity, and quality of life. Clinical parameters will be analysed in specific sub-populations of AGHD patients, defined in protocol section [9.7.2.2](#) as these sub-populations have different starting doses of Sogroya® (somapacitan).

Protocol  
 Study ID: NN8640-4515  
 UTN: U1111-1264-8642  
 EU PAS No: Pending

**CONFIDENTIAL**

Date: 15 February 2022  
 Version: 3.0  
 Status: Final  
 Page: 15 of 53

**Novo Nordisk**

Only data generated as part of routine clinical practice will be collected in this study.

In order to draw clinically relevant conclusions on long-term safety of Sogroya® (somapacitan), the study will compare data from a non-interventional registry (NordiNet® International Outcome Study (IOS)) study which has been monitoring the long-term use of once daily Norditropin® as a historical comparison group consisting of approximately 2300 AGHD patients.

## 8 Research question and objectives

### 8.1 Primary objective

To investigate long-term safety of Sogroya® (somapacitan) therapy in patients with AGHD in the setting of routine clinical practice with special focus on neoplasms and diabetes mellitus type 2.

### 8.2 Secondary objectives

To investigate safety and clinical parameters of Sogroya® (somapacitan) treatment under routine clinical practice in patients with AGHD.

To investigate safety and clinical parameters of Sogroya® (somapacitan) treatment under routine clinical practice in patients with AGHD for the subgroups childhood-onset GHD and females on oral oestrogen therapy, respectively.

To investigate the number of patients achieving the age-adjusted IGF-I SDS levels up to the upper limit of the normal reference range (0 and +2).

To evaluate the impact of Sogroya® (somapacitan) on patient functioning and wellbeing through a patient reported outcome measures (TRIM-AGHD).

### 8.3 Exploratory objective(s)

Change in number of different anti-diabetic medications for patients with diabetes mellitus type 2 at baseline.

To evaluate the impact of Sogroya® (somapacitan) on patient sick days and physician visits, work and study productivity and ability to do regular daily activities through a patient reported outcome measures (AGHD WSI).

## 9 Research methods

### 9.1 Study design

This is a non-interventional, multinational multi-centre, prospective, single-treatment arm, observational PASS in AGHD patients. The study will, under routine clinical practice conditions, investigate the long-term safety of Sogroya® (somapacitan), including but not limited to the occurrence of neoplasm, development of type 2 diabetes and medication errors.

Moreover, the titration regimen and clinical parameters of Sogroya® (somapacitan) therapy in AGHD patients will be collected and evaluated, when available as part of routine clinical practice.

**Figure 1 Study Design**

**Note:** symbol (  ) Represents interim reporting

The study is planned to collect a broad variety of safety and other clinical parameters data generated during routine clinical care visits and other relevant clinical contacts (e.g. phone calls between patient and clinical site) in AGHD patients treated with commercially available Sogroya® (somapacitan). The duration of the study is planned with patient participation for 5 years or longer up to a total study duration of 10 years, if possible. The main purpose of the study is to observe patients for long-term safety. It is however well known that adult patients on GH therapy, often interrupt or discontinue treatment. Due to this expected dropout from treatment, and in the context of the duration of the study, patients switching from or discontinuing treatment with Sogroya® (somapacitan) will be offered continuation in the study in order to collect post treatment data.

The current study will compare data from a non-interventional registry study (NordiNet® IOS) which was monitoring the long-term use of once daily Norditropin® as a historical comparison group consisting of approximately 2300 AGHD patients enrolled in Europe between 2006 and 2016.

The sample size estimation for this study is based on the incidences for neoplasms reported in Nordinet® IOS. It is estimated that a sample size of 400 patients will be required to rule out the doubling of incidence for neoplasms in patients treated with Sogroya® (somapacitan).

Data on concomitant medication, medical history (adult/ childhood onset of GHD), laboratory parameters including but not limited to hepatic, renal, heart and diabetes status as well as data on neoplasms and medication errors will be collected as part of this study if available per routine clinical practice in order to evaluate safety. Other data which are already available in the medical records or being obtained as part of routine clinical practice, such as IGF- I /IGFBP-3 values, measures of body composition and bone health and PROs, will be collected to support the evaluation of clinical parameters.

To enable intra-personal comparison on dose of previous GH treatment, IGF-I/IGFBP-3 SDS values, measures of body composition and bone health and oral oestrogen treatment status, 12-months retrospective data (i.e., from medical charts, where available.) will be collected at study enrolment.

Protocol  
 Study ID: NN8640-4515  
 UTN: U1111-1264-8642  
 EU PAS No: Pending

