**Novo Nordisk**

Additionally, the severity of GH deficiency expressed as IGF-I SDS level prior to any initiation of GH treatment should be collected at baseline, if available.

Data on the number of patients with a minimum of 1-year of follow-up achieving the age-adjusted IGF-I SDS levels up to the upper limit of the normal reference range (0 and +2) will be reported (i) as part of the progress reports in connection with the PSURs - as soon as first data are available and (ii) as part of the interim reporting (data cut 3 and 6 years after FPFV).

Monitoring of safety in this study will be performed from time of enrolment, defined by signing of the informed consent, until the patient's last visit in the study (defined as end of study or withdrawal of informed consent). Adverse events are expected to be captured and reported by the participating sites during routine clinical evaluations (expected every 6-12 months) and any other intermediate contacts with the patient (e.g. phone call etc).

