### 9.2.4 Rationale for selection criteria

The study population is comprised of adult patients diagnosed with GHD and treated with commercially available Sogroya® (somapacitan). The study population will include patients naïve and non-naïve to any GH replacement therapy (including Sogroya® (somapacitan)) at time of study enrolment and will also include patients with severe hepatic impairment, patients with New York

Protocol  
 Study ID: NN8640-4515  
 UTN: U1111-1264-8642  
 EU PAS No: Pending

CONFIDENTIAL

Date: 15 February 2022  
 Version: 3.0  
 Status: Final  
 Page: 20 of 53

Novo Nordisk

Heart Association class 2 heart failure and woman on oral oestrogen treatment who are diagnosed with AGHD.

The few inclusion and exclusion criteria of this study will greatly reduce selection bias. As a multicentre, multinational population has been selected the generalizability of the study is evaluated as high. The study is global and can include all ethnic groups.

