### **9.2.8.6 Medical History**

The information collected for medical history should include diagnosis, date of resolution, as applicable and be recorded at the baseline visit based on discussion with the patient and/or based on medical records. In the event a diagnosis is unknown, the description of symptoms should be recorded.

At least history of cancer/intracranial tumour, history of GHD (childhood onset, adult onset, idiopathic, organic) should be recorded in the eCRF, if available.

To enable intra-personal comparison on dose of previous GH treatment, IGF-I/IGFBP-3 values, measures of body composition and bone health and oral oestrogen treatment status, 12 months of retrospective data (i.e., from medical charts, where available) will be collected at study enrolment. The severity of the GH deficiency (IGF-I level) from when the patient was GH treatment naïve should be collected as part of medical history, if available.

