**CONFIDENTIAL**

Date:	15 February 2022	Novo Nordisk
Version:	3.0	
Status:	Final	
Page:	26 of 53	

treatment when entering the study, details of titration regimen of Sogroya®(somapacitan) should be recorded in the eCRF when available. Patients' adherence will be recorded in the eCRF at each visit by an average missed dose per 2 months ( $\leq 1$  dose,  $1 <$  and  $< 3$  doses or  $3$  doses  $\leq$ ) based on physician asking the patient.

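### The 12-month look-back for comparing previous GH treatment with Sogroya is tied to enrolment, so for patients already on Sogroya it holds partly, or from 12 months' use entirely, Sogroya time

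*Protocol*

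**What the plan says.** Section 9.1 gives the look-back its purpose, which begins "To enable intra-personal comparison on dose of previous GH treatment" and goes on to IGF-I/IGFBP-3 SDS, body composition, bone health and oral oestrogen status. The rule is then "12-months retrospective data (i.e., from medical charts, where available.) will be collected at study enrolment". Section 9.2.8.6 repeats it for nearly the same items: "12 months of retrospective data (i.e., from medical charts, where available) will be collected at study enrolment".

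Three other statements bear on it.
- **Enrolment is consent, not first dose.** Section 9.1: "Monitoring of safety in this study will be performed from time of enrolment, defined by signing of the informed consent".
- **Patients already on Sogroya may enter.** Section 9.2.4 describes a population of "patients naïve and non-naïve to any GH replacement therapy (including Sogroya ® (somapacitan)) at time of study enrolment". The criteria in 9.2.2 and 9.2.3 put no cap on earlier Sogroya use.
- **Both kinds of entrant are expected.** Section 9.2.8.8 says that for patients naïve to Sogroya "treatment when entering the study, details of titration regimen of Sogroya ® (somapacitan) should be recorded in the eCRF when available". The look-back rule makes no such distinction.

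One item reaches further back. Section 9.1 says "the severity of GH deficiency expressed as IGF-I SDS level prior to any initiation of GH treatment should be collected at baseline, if available", and 9.2.8.6 has a matching line.

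**The concern.** The comparison is with the patient's previous GH treatment, so the useful chart period is the one before the first Sogroya dose. The rule instead ties the period to consent. The two coincide for a patient who starts at enrolment. They separate for a patient who has used Sogroya for some time, and the longer the prior use, the less of the earlier treatment the window contains.

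For those patients the comparison would then be empty, or would set Sogroya against Sogroya and could be misread as no change after the switch. This is a data-collection rule. If sites follow it literally, the earlier doses and measurements will not be in the database, and no later analysis plan can supply them. Recruitment runs from 15 Dec 2022 to 15 Dec 2027 (section 6) among users of a marketed product, so prior use of more than 12 months is possible.

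**Working it through.** The protocol gives no figure to reproduce here. The check is the overlap between the look-back window and time on Sogroya.

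**Inputs.** Window of 12 months, taken to end at consent (9.1, 9.2.8.6). Prior Sogroya use of m months at consent, with no upper limit (9.2.2 to 9.2.4). Routine visits expected every 6-12 months (9.1).

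**Overlap for one patient.** Sogroya time in the window = min(m, 12); earlier period = max(0, 12 - m).

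| m (months) | Sogroya time | Earlier period |
|---|---|---|
| 0 | 0 of 12 | 12 of 12 |
| 3 | 3 of 12 | 9 of 12 |
| 6 | 6 of 12 | 6 of 12 |
| 9 | 9 of 12 | 3 of 12 |
| 12 or more | 12 of 12 | 0 of 12 |

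**Across patients already on Sogroya.** The protocol gives no distribution of m. As an assumption, let m be uniform on 0 to M months, with M at least 12.
- Share with no pre-Sogroya time = (M - 12)/M.
- Mean pre-Sogroya time = (12 × 12/2)/M = 72/M months.
- Share with at least one pre-Sogroya visit in the window, for visit spacing V = average of min(1, max(0, 12 - m)/V). For V = 6 this is (6 + 3)/M = 9/M. For V = 12 it is 6/M.

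| M | No pre-Sogroya time | Mean pre-Sogroya months | Visit in window, V = 6 | Visit in window, V = 12 |
|---|---|---|---|---|
| 12 | 0/12 = 0% | 72/12 = 6 | 9/12 = 75% | 6/12 = 50% |
| 24 | 12/24 = 50% | 72/24 = 3 | 9/24 = 37.5% | 6/24 = 25% |
| 36 | 24/36 = 67% | 72/36 = 2 | 9/36 = 25% | 6/36 = 17% |

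These shares refer only to patients already on Sogroya at consent, not to all 400.

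**Does another section collect the missing data?**
- The IGF-I value from before any GH treatment describes the untreated state. It gives no dose, body composition or bone data under the previous product.
- Baseline laboratory, biomarker, body composition and weight values may be at most 6 months old at consent (9.2.7.2, 9.2.7.5, 9.2.7.6, 9.2.8.2), which is a shorter reach than the look-back.
- Section 9.2.8.8 records Sogroya dosing from study entry, and 9.2.8.7 covers medication taken during the study, including at baseline. Neither asks for the dose of a GH product stopped before consent.
- Oral oestrogen is partly covered. Section 9.2.8.7 requires its route, and preferably start and stop dates, for use at visit 1. Only oestrogen stopped before enrolment depends on the look-back.

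**The case against.** The strongest reply is that the text says when the data are collected, not that the 12 months end at consent, and that it names the dose of previous GH treatment as an item wanted. A careful site might therefore look further back. The protocol indeed does not spell out the end of the window. But the 12 months before enrolment is the natural reading, no other anchor is given, and sites in many countries should not have to guess.

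A reader might infer that the look-back is the study's only before-and-after contrast free of the historical cohort. The protocol does not support that. Sections 9.1.1.2.2 and 9.7.2.2 list changes from baseline in IGF-I SDS, bone, body composition and other measures. For patients starting Sogroya at enrolment these are genuine within-patient contrasts.

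It can also be said that no endpoint and no analysis in 9.7 names the retrospective data. The switchers defined in 9.7.2.2 are those who change treatment after enrolment, and for them the present window works. Both statements are true and limit the consequence. They do not remove the purpose that 9.1 and 9.2.8.6 themselves state without restricting it to those patients.

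Finally, the figures depend on an assumed distribution. If no one has used Sogroya for more than 12 months at consent, no patient loses the whole window. That is why the range starts at 0%.

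**Conclusion.** The point holds within limits. On the natural reading of 9.1 and 9.2.8.6, patients already on Sogroya at consent give a mixed window if they have under 12 months' use, and no previous-treatment data if they have 12 months or more. Among these patients the share with no pre-Sogroya time is 0%, 50% or 67% under uniform prior use over 0-12, 0-24 or 0-36 months. That distribution is an assumption, and the size of the subgroup is not stated, so no figure can be given for the whole study.

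Patients starting at or after enrolment, the primary safety endpoints and the planned 400 patients are untouched. It would go too far to conclude that the study loses its within-patient information in general, or that oestrogen status goes unrecorded at entry. The case for acting is that the data-collection rule misses its stated purpose for a group the protocol expressly admits, and that the gap cannot be repaired at the analysis stage.

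**What to change.** In 9.1 and 9.2.8.6, keep the present 12-month window and state that it ends at consent. For patients already on Sogroya at consent, add to it: collect, where available, the date of the first Sogroya dose and the 12 months of chart data before that date (previous GH dose, IGF-I/IGFBP-3, body composition, bone health, oral oestrogen status). The new window must not replace the present one. For a patient 18 months on Sogroya, moving the window would collect months 30 to 18 before consent and drop the latest 12 months that the rule now gathers.

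Base the comparison of previous GH treatment with Sogroya only on patients who have pre-Sogroya data, and report how many there are.

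The cost is wording in two sections and an eCRF field with a completion instruction. The small downside is that sites must search further back in the charts of these patients.
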